## 1. Background

The current treatment of chronic hepatitis C (CHC) with pegylated interferons plus ribavirin achieves a sustained response in less than 50% of all patients (1, 2). Over the last 10 years, several research groups including our own studied the apparent interferon resistance caused by hepatitis C virus (HCV). These studies have revealed an amazing ability of HCV to interfere with and inhibit the innate immunity, specifically the interferon system. Type I interferons (IFNαs and IFNβ) are induced upon viral infection through the activation of a pathway involving RIG-I, TBK1, IKK $\varepsilon$ , IRF3 and NF $\kappa$ B (3-9). They are then secreted and can bind to the IFN $\alpha$ receptor (IFNAR) on the same cell (autocrine amplification loop) or on neighboring cells (paracrine amplification loop), or can be transported through the blood circulation to distant sites. IFN binding to IFNAR activates the Jak-STAT signal transduction pathway (10, 11). Activated STAT1 (signal transducer and activator of transcription) and STAT2 stimulate the transcription of several hundreds of ISGs (IFN stimulated genes). Amongst them are genes that are important to establish an antiviral state in the cells, but also additional IFN\alpha genes, and IRF7, an important transcription factor for the activation of IFNα genes. This positive feedback loop results in a strong antiviral response by the host.

HCV targets this system at three levels. First, the viral non structural protein 3/4 (NS3/4) inhibits RIG-I (12). Second, NS3/4 proteolytically cleaves TRIF, an adaptor protein linking Toll-like receptor 3 to IFN gene induction (13). In both cases, the induction of IFN expression by HCV infected cells is blocked. Third, HCV interferes with IFN induced signaling through the Jak-STAT pathway. Our own research group has focused their studies on this third mechanism of HCV interference with the IFN system. A key finding, published in the Journal of Virology 1999, was the observation that interferon induced activation and binding of ISGF3 and of STAT1 dimers is inhibited in cells that express HCV proteins (14). ISGF3 (interferon stimulated gene factor 3) and STAT1 (signal transducer and activator of transcription 1) are essential for interferon signal transduction. Both mice and human patients that lack STAT1 have a severe impairment of the interferon system and susceptible to (viral) infections (15-17).

A detailed analysis of the molecular mechanisms responsible for the inhibition of Jak-STAT signaling by HCV revealed a novel mechanism of viral interference with IFN signaling. HCV infection induces the expression of protein phosphatase 2A (PP2A) (18). PP2A is a direct inhibitor of protein arginine methyltransferase 1 (PRMT1) (19), PRMT1 is responsible for arginine methylation of STAT1, an important posttranslational modification that controls the association of STAT1 with its inhibitor PIAS1 (protein inhibitor of activated STAT1)(20). Therefore, by inducing the expression of PP2A, HCV indirectly induces the binding of PIAS1 to STAT1 (Figure 1). As a consequence, ISGs that are susceptible to inhibition of STAT1 by PIAS1 are not induced (19, 21).

[figure not shown]

Figure 1: Binding of STAT1 to response elements in the promotors of IFN stimulated genes (ISG) is controlled by PIAS1 (protein inhibitor of activated STAT1). PIAS1 can bind to unmethylated STAT1 dimers (left side of figure), but not to methylated STAT1 dimers (right side of figure). HCV inhibits the methylation of STAT1 by inducing PP2A, a direct inhibitor of PRMT1.

The reaction equilibrium of PRMT1 can be driven to the product side (methylated substrates, for example methylated STAT1) by increasing the concentration of the substrates. S-Adenosyl-L-Methionine (AdoMet) is the methyl group donor in the reaction. Its concentration can be increased by adding AdoMet to the reaction in vitro or by adding AdoMet to the culture medium of cells. AdoMet is recycled in a cycle that uses betaine as a substrate for betaine homocysteine methyltransferase (Figure 2), and the concentration of AdoMet can also be increased by adding betaine.

[figure not shown]

Figure 2: S-Adenosyl-L-Methionine is the methyl group donor in methylation reactions catalysed by PRMT1 (for example methylation of STAT1). S-Adenosyl-L-Methionine is recycled from L-Homocysteine through Methionine. Betaine is a substrate of Betaine-Homocysteine-Methyltransferase.

In as yet unpublished work, we found that the treatment of cells with the methyl group donors S-adenosylmethionine (AdoMet) and betaine restores the sensitivity to IFN $\alpha$  in cells that express HCV proteins. Furthermore, in Huh7 cells harboring a HCV replicon, the inhibitory effect of IFN $\alpha$  on the replicon was ten times stronger when the cells were treated with IFN $\alpha$  plus AdoMet and betaine. Both AdoMet and betaine have been used in human for many years, and are over the counter drugs in many countries (not Switzerland). They are used for a number of indications such as alcoholic liver disease, non-alcoholic liver disease or hyperhomocysteinemia. They are taken orally, and have an excellent safety record.

Based on our result using biochemical assays, cell culture assays with cells expressing HCV proteins, and Huh7 cells harboring a HCV replicon we hypothesize that adding AdoMet and betaine to the current standard therapy with pegylated IFN $\alpha$  plus ribavirin can enhance the efficacy of the treatment, and will result in sustained responses even in patients that have been non-responders or relapser to (peg-)IFN $\alpha$  plus ribavirin treatments.

## 2. Rational of the Study

- 50-60% of patients with chronic hepatitis C are not cured by treatment with pegylated IFNα plus ribavirin.
- Retreatment of non-responders of previous (pegylated) IFN $\alpha$  plus ribavirin therapies with pegylated IFN $\alpha$  plus ribavirin results in a sustained response in less than 10% of the patients.
- Extensive analysis of IFNα signaling in cells expressing HCV proteins, in transgenic mice expressing HCV proteins, and in liver biopsies from patients with chronic hepatitis C point to STAT1 methylation as an important posttranslational modification targeted by HCV to inhibit IFNα signaling.
- STAT1 methylation can be increased and IFNα can be improved by adding AdoMet and betaine.
- Analysis of mRNA expression levels of interferon stimulated genes (ISGs) in PBMCs (RNA extracted from whole blood) can be used as a surrogate marker for the activation of the IFN system.

## 3. Objectives of the Study

The study is designed to test the hypothesis that a combination treatment with pegylated IFN $\alpha$ 2b, ribavirin, AdoMet and betaine is superior to the current standard combination therapy with pegylated IFN $\alpha$  plus ribavirin.

## 4. Experimental Design

Prospective, randomized, open label pilot study to test the efficacy and safety of a combination treatment with PegIntron, Rebetol, AdoMet and betaine in **non-responders** 

of previous combinations therapy with (peg)IFNα and Ribavirin.

Half of the patients (Group A) will be treated during the first week with AdoMet and Betaine, followed by a combination treatment of PegIntron, Rebetol, AdoMet and Betaine.

The other half of the patients (Group B) will be treated during the first 1 week with PegIntron and Rebetol, followed by a combination treatment of PegIntron, Rebetol, AdoMet and Betaine. (This randomized assignment to groups A or B will allow to test the usefulness of the surrogate marker ISG induction for predicting treatment response). The randomization will be done in two separate groups for genotype 1 and 4 and for genotypes 2 and 3, respectively. In each group, a list with a randomized sequence of A's and B's in blocks of 10 will be used to assign the patients into groups A or B.

The study will be performed at the University Hospital Basel.

#### 5. Patient Selection

#### **Number of patients:**

30 patients, non-responders to previous (peg-)IFNα - Ribavirin combination therapy

#### **Inclusion criteria:**

- Male and female between 18 and 65 years.
- Non-responders in previous treatments with IFN $\alpha$  plus ribavirin or pegylated IFN $\alpha$  plus ribavirin.
- Elevated ALT-levels on at least two occasions during  $\geq 6$  months preceding entry.
- Detection of HCV RNA in serum (PCR).
- Compensated liver disease (Child-Pugh A) and a Child-Pugh score ≤5.
- The following minimal hematologic and biochemical criteria:
- Hemoglobin for males and females  $\geq 11g/dl$
- Absolute Neutrophil count ≥1500 cells/mm^3
- Platelets  $> 75'000/\text{mm}^3$
- HBs Ag negative.
- ANA  $\leq 1.320$ , and no evidence for autoimmune hepatitis.
- $\alpha$ -Fetoprotein  $\leq 50 \mu g/l$  (when between upper limit of normal and  $50 \mu g/l$ , ultrasonographical exclusion of hepatocellular carcinoma (HCC) is needed).
- Fasting blood glucose within normal limits, if history of diabetes or hypertension, a pre-therapy ocular examination is indicated.
- TSH within normal limits or adequately controlled.
- Negative urine or blood pregnancy test (for women of childbearing potential) documented within the 2-3 week period prior to the first dose of study drug. Additionally, all fertile males and females must be using effective contraception during treatment and during the 6 months after treatment end. This may include, but is not limited to, using birth control pills, IUDs, condoms, diaphragms, or implants, being surgically sterilized, or being in a post-menopausal state.
- Willingness to give written informed consent and willingness to participate to and comply with the study.

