## 10. Study Medication and Treatment:

## 10.1. Supply and Drug Dispensing

#### 10.1.1. AdoMet and Betaine

AdoMet (Samyr ®) and Betaine (Cystadane ®) will be supplied by the Pharmacy of the University Hospital Basel.

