### 10.2. Treatment of Group A Patients:

**Dosage** (dose adjustment guidelines: see Appendix 3): patients included will receive one week of pretreatment with:

1. AdoMet  $3 \times 400 \text{mg/d p.o.}$ 

2. Betaine  $2 \times 3g/d \text{ p.o.}$ 

Followed by a combination treatment with:

- 1. PEG-interferon alfa-2b (PegIntron®): 1.5μg/kg bodyweight s.c./week (independent of genotype) plus
- 2. Ribavirin (Rebetol®):

BW <65 Kg: 800 mg QD (2 capsules in the morning + 2 capsules in the evening)

BW 65-85 Kg: 1,000 mg QD (2 capsules in the morning + 3 capsules in the evening)

BW >85 Kg: 1,200 mg QD (3 capsules in the morning + 3 capsules in the evening)

3. AdoMet 3 x 400mg/d p.o.

4. Betaine  $2 \times 3g/d \text{ p.o.}$ 

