### 10.3. Treatment Group B Patients:

Patients will receive one week of treatment with PegIntron and Rebetol, followed by a combination treatment with PegIntron, Rebetol, AdoMet and betaine. The dosages are identical to group A.

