#### 12.2.1 Management of Adverse Events

Subjects having AEs will be monitored with relevant clinical assessments and laboratory tests, as determined by the investigator. The investigator is expected to report ongoing AEs at completion of the clinical study to the primary care physician who will determine the need for and provide standard medical care.

Any actions taken and follow-up results must be recorded either on the appropriate page of the CRF or in a follow-up letter to ESSEX Chemie AG as well as in the subject's source documentation. Follow-up laboratory results should be filed with the subject's source documentation.

For all AEs that require the subject to be discontinued from the study, relevant clinical assessments and laboratory tests will be repeated on at least a monthly basis until final resolution or stabilization of the event(s).

Adverse events can be managed by dose reduction of one or both study medications. In the case of life-threatening AEs as described in Section 12.2.4 both PEG-Intron plus REBETOL must be discontinued permanently.

Reduced doses will be achieved by decreasing the injection volume of the PEG-Intron and the number of capsules/tablets of REBETOL as referenced in Table 1 and Table 2. While at a reduced dose level, the subject should return for assessment at a minimum of every two weeks until the AE resolves or the subject is stable. If the AE persists but does not fall into the range for permanent discontinuation, the reduced dose of PEG-Intron and/or ribavirin (whichever has been reduced) may be continued. At the discretion of the investigator, the dose of PEG-Intron and/or ribavirin may be increased to full dose, directly or in steps, when the AE subsides. If the AE recurs, the subject should be maintained at the previously tolerated reduced dose or, at the discretion of the investigator, discontinue treatment.

Table 1 Dose Reduction for REBETOL

Screening Weight a	Full Daily Dose	First Reduced Dose	First Reduced Number of Capsules	Second Reduced Dose	Second Reduced Number of Capsules
40-65 kg	800 mg/day	600 mg/day	1 in AM/2 in PM	400 mg/day	1 in AM/1 in PM
>65-85 kg	1000 mg/day	800 mg/day	2 in AM/2 in PM	600 mg/day	1 in AM/2 in PM
>85-105 kg	1200 mg/day	1000 mg/day	2 in AM/3 in PM	800 mg/day	2 in AM/2 in PM
>106-125 kg	1400 mg/day	1000 mg/day	2 in AM/3 in PM	800 mg/day	2 in AM/2 in PM

a: Use standard rounding procedures: for 0.1-0.4 kg, round down and 0.5-0.9 kg, round up.

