## Appendix 1a: Schedule of Assessments in group A

	Baseline	At the end of 1 week of AdoMet- Betaine (pre-)	During full combination treatment after 1, 2, 4 days, 1, 2, 4, 6, 8, 12 weeks, thereafter every 6 weeks	Follow-up 6 months after end of treatment
		treatment	until end of treatment	
Medical history	X			
Adverse Events / Tolerability	X	X	X	X
Physical Exam / Vital Signs	X	X	X	X
Concomitant Medication	X	X	X	X
Hematology	X	X	X	X
Blood chemistry	X	X	X	X
Quick / INR	X			
AFP	X			
ANA	X			
TSH	X		X (a)	X
HBs Ag, HAV- IgM, HIV-test	X			
Liver biopsy	X (b)			
Urinanalysis	X			
Pregnancy Test	X		X (c)	X
HCV genotype	X			
HCV RNA	X	X	X (d)	X
quantitative				
Isolation of	X	X	X (e)	
leucocytes and				
asservation of				
serum				

- (a) only at week 12, 24 and 48
- (b) if not done within 12 months prior to study entry
- (c) every 4 weeks
- (d) at day 1, 2, 4, week 1, 2, 4, 8, 12, 24, 48
- (e) at day 1, 2, 4 (24hours, 48hours, 96hours), week 1 after first injection of PegIntron, then weeks 2, 4, 6, 8, 12, 24, 48

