## Appendix 1b: Schedule of Assessments in group B

	Baseline	During treatment	During treatment often	Follow up 6
	Daseime	0	During treatment after	Follow-up 6
		with PegIntron and	1, 2, 4, 6, 8, 12 weeks,	months after
		Ribavirin (first	thereafter every 6	end of
		week) after 1,2,4	weeks until end of	treatment
		days	treatment	
Medical history	X			
Adverse Events /	X		X	X
Tolerability				
Physical Exam /	X		X	X
Vital Signs				
Concomitant	X		X	X
Medication				
Hematology	X		X	X
Blood chemistry	X		X	X
Quick / INR	X			
AFP	X			
ANA	X			
TSH	X		X (a)	X
HBs Ag, HAV-	X			
IgM, HIV-test				
Liver biopsy	X (b)			
Urinanalysis	X			
Pregnancy Test	X		X (c)	X
HCV genotype	X			
HCV RNA	X	X (e)	X (d)	X
quantitative		. ,		
Isolation of	X	X	X (f)	
leucocytes and				
asservation of				
serum				
	2 24 1	40	I .	ı

- (a) only at week 12, 24 and 48
- (b) if not done within 12 months prior to study entry
- (c) every 4 weeks
- (d) at the end of weeks 1, 2, 4, 8, 12, 24, 48
- (e) at the end of the first week (PegIntron-Rebetol only)
- (f) at day 1, 2, 4 (24hours, 48hours, 96hours), week 1 after first injection of PegIntron, then weeks 2, 4, 6, 8, 12, 24, 48

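### Group A has no scheduled pregnancy test between Baseline and its first ribavirin dose, although a suitable visit already exists

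*Protocol*

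**What the plan says.** Protocol section 5 (Inclusion criteria) asks women of childbearing potential for a negative urine or blood pregnancy test "documented within the 2-3 week period prior to the first dose of study drug". It also requires effective contraception during treatment and for 6 months afterwards. The exclusion criteria rule out ongoing pregnancy, and section 9.1 lists pregnancy among the reasons to end participation.

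The two groups reach ribavirin at different times. For Group A, section 10.2 states that "patients included will receive one week of pretreatment with" AdoMet and betaine, with PegIntron and Rebetol following. For Group B, section 10.3 states: "Patients will receive one week of treatment with PegIntron and Rebetol".

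Appendix 1a gives Group A an end-of-pretreatment visit, whose column heading begins "At the end of 1 week of AdoMet- Betaine (pre". Adverse events, physical examination, concomitant medication, hematology, blood chemistry and quantitative HCV RNA are all marked there. The pregnancy-test row is marked at Baseline, left blank at this visit, marked at four-weekly intervals during full combination treatment, and marked at follow-up. Appendix 1b has the same four-weekly rule for Group B ("c) every 4 weeks").

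**The concern.** The Protocol takes pregnancy seriously: it excludes pregnant women and male partners of pregnant women, requires contraception, and retests regularly during treatment. One would expect a negative result close to the moment when ribavirin starts. In Group B the Baseline test can serve that purpose, because the first dose of any study drug is also the first Rebetol dose. In Group A a week of AdoMet and betaine comes in between, and the visit that ends that week omits the test. The first on-treatment test falls in the full-combination column, so it comes after Rebetol has begun.

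At stake is the possible start of ribavirin in a woman whose pregnancy was missed by, or began after, the Baseline test. The efficacy analysis is not involved.

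**Working it through.** The Protocol gives no figure for the age of the test at first ribavirin, so there is nothing to reproduce. Simple interval arithmetic is enough.

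**Inputs**
- Test window W: 14 or 21 days, since section 5 gives 2-3 weeks without choosing.
- Days from first study drug of any kind to first Rebetol, P: 7 in Group A (sections 4 and 10.2) and 0 in Group B (section 10.3).
- Days from the Baseline test to the first dose of any study drug, d: not stated. Baseline is not dated relative to dosing, so d is varied from 0 to W. Baseline is assumed to fall on or before the first dose.

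**Formula.** Age of the last scheduled test at first Rebetol = d + P.

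| d (days) | Group A: d + 7 | Group B: d + 0 |
|---|---|---|
| 0 | 7 | 0 |
| 14 | 21 | 14 |
| 21 | 28 | 21 |

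**Window counted to the first dose of any study drug (d ≤ W).** With W = 21 the range is 7 to 28 days in Group A and 0 to 21 in Group B. With W = 14 it is 7 to 21 and 0 to 14.

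**Window counted to the first PegIntron/Rebetol dose.** Group A must then satisfy d + 7 ≤ W, so d ≤ 14 (W = 21) or d ≤ 7 (W = 14). The maximum age is W, that is 21 or 14 days, in both groups. The minimum in Group A is still 7 days.

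**Result common to both readings.** Group A's last scheduled test is never less than 7 days old at first Rebetol; Group B's can be done on the same day.

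**Comparison with the Protocol's own interval.** Four-weekly testing on treatment is 4 × 7 = 28 days. Group A's worst case of 28 days equals that interval and does not exceed it.

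**The case against.** The strongest reply is that nothing in the Protocol is violated. A protocol that accepts 28 days between tests during ribavirin exposure is consistent in accepting at most 28 days before it. Contraception is required during treatment, and section 10.2 makes the AdoMet/betaine week part of Group A's treatment. The 28-day figure is the most the wording allows: if Baseline is close to dosing, the test is about 7 days old. Unscheduled visits for clinical safety are allowed under section 11. The number of women of childbearing potential among the 30 patients is not given, so no expected harm can be calculated. All of this stands, and it keeps the point minor. It does not explain why the check is left out at a visit where blood is already taken.

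A reader might infer more from the wording of section 5, and three stronger readings should be set aside.

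- *That the entry rule is contradictory.* The 2-3 week window is imprecise and the term for study drug is undefined. But any test within 2 weeks meets both limits, and no other section gives a conflicting number.
- *That eligibility depends on an allocation made only after inclusion (section 8).* This needs the term to mean PegIntron and Rebetol alone. The main support is the sentence "Adverse events can be managed by dose reduction of one or both study medications", which comes from text about reducing those two drugs and is thin evidence for how an inclusion criterion should be read. The heading "10. Study Medication and Treatment" covers all four agents, and on that reading the dependence disappears.
- *That the window should be re-anchored to the first Rebetol dose.* In Group A, a test at the end of pretreatment would then satisfy an inclusion criterion only after randomization and a week of dosing.

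**Conclusion.** The point holds as a minor patient-safety improvement. Appendix 1a schedules no pregnancy test between Baseline and Group A's first Rebetol dose, which comes 7 days after the first AdoMet/betaine dose. The last scheduled test is then at least 7 days old, and up to 28 days if a 3-week limit is counted to first AdoMet, against 0 to 21 days in Group B.

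The lower bound of 7 days assumes only that Baseline is on or before the first AdoMet dose. The upper bound also assumes the 3-week limit, counting to any study drug, and a test done as early as that allows. It is a permitted maximum and says nothing about usual practice. No stated limit is breached, and no endpoint or sample-size figure changes.

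**What to change.** 1. In Appendix 1a, mark the pregnancy-test row at the existing end-of-pretreatment visit and require a negative result before the first Rebetol dose. Describe this as a pre-ribavirin safety check, separate from the inclusion criterion. If the visit falls on the day Rebetol starts, the test age in Group A drops from 7-28 days to about 0.
2. In section 5, keep the Baseline test as the eligibility test and state one maximum age for both groups, for example no more than 3 weeks before the first dose of any study drug. Eligibility is then settled before randomization and does not depend on the group assigned.

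The cost is one reworded criterion and one urine or blood test per woman of childbearing potential in Group A, with no added visit. The downside is a rare exit under section 9.1, in Group A only, before the first PegIntron injection. Such a woman would contribute no data to the ISG comparison of Groups A and B in section 7.2, but the Protocol's own pregnancy rules mean that she should not start ribavirin in any case.

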#### **Exclusion criteria:**

- Women with ongoing pregnancy or breast feeding.
- Positive test at screening for anti-HAV IgM Ab, HBsAg, anti-HBc IgM Ab, HBe Ag.
- Positive test at screening for HIV.
- History or other evidence of a medical condition associated with chronic liver disease other than HCV (e.g., hemochromatosis, autoimmune hepatitis, alcoholic liver disease, toxin exposures).
- Hypersensitivity to study drugs.
- Participation in any other clinical trial within 30 days of entry into this protocol.
- Treatment with any investigational drug within 30 days of entry into this protocol.

- History or evidence of decompensated liver disease (Child-Pugh B/C) and a Child-Pugh score >5. Ascites, coagulopathy, hyperbilirubinemia, hepatic encephalopathy, or hypoalbuminemia and a Child-Pugh score >5 are conditions consistent with decompensated liver disease.
- History or other evidence of bleeding from esophageal varices or other conditions consistent with decompensated liver disease.
- Hepatocellular carcinoma (HCC) or α-Fetoprotein >50µg/l.
- Patients with organ transplants other than cornea and hair transplant.
- Therapy with any antisystemic or immunmodulatory treatment (including supraphysiologic doses of steroids or radiation) ≤6 months prior the first dose of study drug
- Hemoglobinopathy (e.g. thalassemia) or any other cause of or tendency for hemolysis.
- Any known preexisting medical condition that could interfere with the patient's participation in and completion of the study such as:
- Preexisting psychiatric condition, especially depression, or a history of severe psychiatric disorder, such as major psychosis, suicidal ideation and/or suicidal attempts (based on a mandatory psychiatric advice).
- CNS trauma or active seizure disorders requiring medication.
- Significant cardiovascular dysfunction.
- Poorly controlled diabetes mellitus.
- Renal dysfunction, i.e. serum creatinine levels  $\geq 1.5$  times upper limit of normal.
- Autoimmune diseases.
- Evidence of severe retinopathy (e.g. CMV retinitis, macular degeneration).
- Any medical condition requiring, or likely to require during the course of the study, chronic systemic administration of steroids.
- Clinical gout.
- Important substance abuse (alcohol >80 g/d, i.v. drugs etc.).
- Active opportunistic infections.
- Non-Hodgkin lymphoma or Hodgkin lymphoma.
- Kaposi sarcoma.
- Inability or unwillingness to provide informed consent or abide by the requirements of the study.
- Male partners of pregnant women.

